10.4.3.2. Derivations and Handling of Missing Baseline Data

Definition	Reporting Details
Change from Baseline	= Post-Dose Visit Value – Baseline

NOTES:

- Unless otherwise specified, the baseline definitions specified in Section 10.4.3.1 Baseline Definitions will be used for derivations for endpoints / parameters and indicated on summaries and listings.
- Unless otherwise stated, if baseline data is missing no derivation will be performed and will be set to missing.
- The baseline definition will be footnoted on all change from baseline displays.

10.4.4. Reporting Process & Standards

Reporting Process	
Software	

 The currently supported versions of SAS software will be used. 	
Reporting Area	
HARP Server	: uk1salx00175
HARP Area	Part1:/arenv/arprod/gsk1325756/mid206817/primary_01 Part2:/arenv/arprod/gsk1325756/mid206817/final_01
QC Spreadsheet	Part1:/arenv/arprod/gsk1325756/mid206817/primary_01/qc Part2:/arenv/arprod/gsk1325756/mid206817/final_01/qc
Analysis Datasets	

 Analysis datasets will be created according to GSK IDSL A&R dataset standards 	
Generation of RTF Files	

 N/A 	

Reporting Standards	
General	

 The current GSK Integrated Data Standards Library (IDSL) will be applied for reporting, unless otherwise stated: 
 4.03 to 4.23: General Principles 5.01 to 5.08: Principles Related to Data Listings 6.01 to 6.11: Principles Related to Summary Tables 7.01 to 7.13: Principles Related to Graphics 	
Formats	

 All data will be reported according to the actual treatment the subject received unless otherwise stated. GSK IDSL Statistical Principles (4.24) for decimal places (DP's) will be adopted for reporting of data based on the raw data collected. Numeric data will be reported at the precision collected on the eCRF. The reported precision from non eCRF sources will follow the IDSL statistical principles but may be adjusted to a clinically interpretable number of DP's. 	
Planned and Actual Time	

 Reporting for tables, figures and formal statistical analyses: 
 Planned time relative to dosing will be used in figures, summaries, statistical analyses and calculation of any derived parameters, unless otherwise stated. The impact of any major deviation from the planned assessment times and/or scheduled visit days on the analyses and interpretation of the results will be assessed as appropriate. Reporting for Data Listings: 
 Planned and actual time relative to study drug dosing will be shown in listings (Refer to IDSL Statistical Principle 5.05.1). Unscheduled or unplanned readings will be presented within the subject's listings. Visits outside the protocol defined time-windows (i.e. recorded as protocol deviations) will be included in listings but omitted from figures, summaries and statistical analyses. 	
Unscheduled Visits	

 Unscheduled visits will not be included in summary tables. Unscheduled visits will not be included in figures. All unscheduled visits will be included in listings. 	
Descriptive Summary Statistics	
Continuous Data	Refer to IDSL Statistical Principle 6.06.1
Categorical Data	N, n, frequency, %
Reporting of Pharmacokinetic Concentration Data	
Descriptive Summary Statistics	Refer to IDSL Statistical Principle 6.06.1 Assign zero to NQ values (Refer to GUI_51487 for further details)

Reporting Standards	
Reporting of Pharmacokinetic Parameters	
Descriptive Summary Statistics. (Log Transformed)	N, n, geometric mean, 95% CI of geometric mean, standard deviation (SD) of logged data and between geometric coefficient of variation (CVb/w (%)) will be reported. $CVb (\%) = \text{SQRT} (\exp(SD^2) - 1) * 100$ (SD = SD of loge-transformed data) $CVw (\%) = \text{SQRT} (\exp(MSE) - 1) * 100$ (MSE = mean square error from mixed effect model of loge-transformed data).
Parameters Not Being Log Transformed	tmax, tlag, tlast
Parameters Not Being Summarised	The following PK parameters will not be summarised but listed: %AUCex, lambda_z, lambda_z_lower, lambda_z_upper, #pts, R2.
Graphical Displays	

 Refer to IDSL Statistical Principles 7.01 to 7.13. 	

Reporting Standards

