10.5. Appendix 5: Derived and Transformed Data
10.5.1. General

Multiple Measurements at One Time Point
 
 Mean of the measurements will be calculated and used in any derivation of summary statistics but if listed, all data will be presented. If there are two values within a time window the value closest to the target day for that window will be used. If values are the same distance from the target, then the mean will be taken. Subjects having both High and Low values for Normal Ranges at any post-baseline visits for safety parameters will be counted in both the High and Low categories of “Any visit post-baseline” row of related summary tables. This will also be applicable to relevant Potential Clinical Importance summary tables.
Study Day

 Calculated as the number of days from start of dosing date: 
 Ref Date = Missing → Study Day = Missing Ref Date < of start of dosing Date → Study Day = Ref Date – of start of dosing Date Ref Date ≥ of start of dosing Date → Study Day = Ref Date – (of start of dosing Date) + 1

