10.9.5. Safety Tables

Safety: Tables					
No.	Population	IDSL / TST ID / Example Shell	Title	Programming Notes	Deliverable [Priority]
Adverse Events (AEs)					
2.1.	Safety	AE1	Summary of All Adverse Events by System Organ Class and Preferred Term (Part 1)		PR [1]
2.2.	Safety	AE5A	Summary of All Adverse Events by Maximum Intensity (Part 1)		PR [1]
2.3.	Safety	AE1	Summary All Drug-Related Adverse Events by System Organ Class and Preferred Term (Part 1)		PR [1]
2.4.	Safety	AE5A	Summary All Drug-Related Adverse Events by Maximum Intensity (Part 1)		PR [1]
2.5.	Safety	AE1	Summary of All Adverse Events by System Organ Class and Preferred Term (Part 2)		SAC [2]
2.6.	Safety	AE5A	Summary of All Adverse Events by Maximum Intensity (Part 2)		SAC [2]
2.7.	Safety	AE1	Summary All Drug-Related Adverse Events by System Organ Class and Preferred Term (Part 2)		SAC [2]
2.8.	Safety	AE5A	Summary All Drug-Related Adverse Events by Maximum Intensity (Part 2)		SAC [2]
Laboratory: Chemistry					
2.9.	Safety	LB1	Summary of Chemistry (Part 1)		PR [1]
2.10.	Safety	LB1	Summary of Chemistry Changes from Baseline (Part 1)		PR [1]
2.11.	Safety	LB4	Summary of Chemistry Data Shifts from Baseline with Respect to the Normal Range (Part 1)		PR [1]
2.12.	Safety	LB1	Summary of Chemistry (Part 2)		SAC [2]
2.13.	Safety	LB1	Summary of Chemistry Changes from Baseline (Part 2)		SAC [2]

Safety: Tables					
No.	Population	IDSL / TST ID / Example Shell	Title	Programming Notes	Deliverable [Priority]
2.14.	Safety	LB4	Summary of Chemistry Data Shifts from Baseline with Respect to the Normal Range (Part 2)		SAC [2]
Laboratory: Hematology					
2.15.	Safety	LB1	Summary of Hematology (Part 1)		PR [1]
2.16.	Safety	LB1	Summary of Hematology Changes from Baseline (Part 1)		PR [1]
2.17.	Safety	LB4	Summary of Hematology Data Shifts from Baseline with Respect to the Normal Range (Part 1)		PR [1]
2.18.	Safety	LB1	Summary of Hematology (Part 2)		SAC [2]
2.19.	Safety	LB1	Summary of Hematology Changes from Baseline (Part 2)		SAC [2]
2.20.	Safety	LB4	Summary of Hematology Data Shifts from Baseline with Respect to the Normal Range (Part 2)		SAC [2]
Laboratory: Urinalysis					
2.21.	Safety	UR3b	Summary of Urinalysis Data (Glucose, Protein, Blood, Ketones, Bilirubin, Urobilinogen) (Part 1)		PR [1]
2.22.	Safety	LB1	Summary of Urinalysis Data (Specific Gravity and pH) (Part 1)		PR [1]
2.23.	Safety	UR3b	Summary of Urinalysis Data (Glucose, Protein, Blood, Ketones, Bilirubin, Urobilinogen) (Part 2)		SAC [2]

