2.24.	Safety	LB1	Summary of Urinalysis Data (Specific Gravity and pH) (Part 2)		SAC [2]
ECG					
2.25.	Safety	EG1	Summary of ECG Findings (Part 1)		PR [1]
2.26.	Safety	EG2	Summary of ECG Value (Part 1)		PR [1]
2.27.	Safety	EG2	Summary of Change from Baseline in ECG Values (Part 1)		PR [1]
2.28.	Safety	EG1	Summary of ECG Findings (Part 2)		SAC [2]

CONFIDENTIAL

206817

Safety: Tables					
No.	Population	IDSL / TST ID / Example Shell	Title	Programming Notes	Deliverable [Priority]
2.29.	Safety	EG2	Summary of ECG Value (Part 2)		SAC [2]
2.30.	Safety	EG2	Summary of Change from Baseline in ECG Values by Visit (Part 2)		SAC [2]
Vital Signs					
2.31.	Safety	VS1	Summary of Vital Signs (Part 1)		PR [1]
2.32.	Safety	VS1	Summary of Change from Baseline in Vital Signs (Part 1)		PR [1]
2.33.	Safety	VS1	Summary of Vital Signs (Part 2)		SAC [2]
2.34.	Safety	VS1	Summary of Change from Baseline in Vital Signs (Part 2)		SAC [2]

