			Week 24	55	-3.3	29.50	0	-235	36
	Trt B	220	Week 8	150	-1.2	16.32	0	-320	38
			Week 12	133	0.7	10.55	1	-64	32
			Week 24	55	-3.3	29.50	0	-235	36

USER ID: directory/program.sas DDMMYYYY hh:mm

CONFIDENTIAL

206817

Example: LB4

Protocol: GSK123456

Population: xxxxx

Page 1 of n

Table x.x
xxxxxxxxxxxxxxxxxxxxxxxxxxxxxx

Test= Alanine Aminotransferase (IU/L), Treatment=Treatment A

Planned Time	N	n	Baseline Value	Time Period Value				
				High	Normal	Low	Total	
Week 1	100	100	High	0	1 (1%)	3 (3%)	4 (4%)	
			Normal	10 (10%)	84 (84%)	2 (2%)	96 (96%)	
			Low	0	0	0	0	
			Total	10 (10%)	85 (85%)	5 (5%)	100 (100%)	
Week 4	100	100	High	0	1 (1%)	3 (3%)	4 (4%)	
			Normal	10 (10%)	84 (84%)	2 (2%)	96 (96%)	
			Low	0	0	0	0	
			Total	10 (10%)	85 (85%)	5 (5%)	100 (100%)	
Worst Case Post-Baseline	100	100	High	0	1 (1%)	3 (3%)	4 (4%)	
			Normal	10 (10%)	84 (84%)	2 (2%)	96 (96%)	
			Low	0	0	0	0	
			Total	10 (10%)	85 (85%)	5 (5%)	100 (100%)	

USER ID: directory/program.sas DDMMYYYY hh:mm

CONFIDENTIAL

206817

Example: UR3b
Protocol: GSK123456
Population: xxxxx

Page 1 of n

Table x.x
xxxxxxxxxxxxxxxxxxxxxxxxxxxxxx

Test	Period/Planned Relative Time	Result	Treatment A (N=100)		Treatment B (N=100)	
			Count	(%)	Count	(%)
Urine General Dipstick	SCREENING/ SCREENING	Positive	30	(30%)	60	(60%)
		Negative	40	(40%)	30	(30%)
		No Result	30	(30%)	10	(10%)
	PERIOD 1/DAY 1	Positive	40	(40%)	50	(50%)
		Negative	30	(30%)	40	(40%)
		No Result	30	(30%)	10	(10%)
Urine Occult Blood (Dipstick)	SCREENING/ SCREENING	None	40	(40%)	40	(40%)
		Trace	25	(25%)	25	(25%)
		1+	10	(10%)	15	(15%)
		2+	0		0	
		3+	0		0	
		No Result	10	(10%)	20	(20%)
	PERIOD 1/DAY 1	None	40	(40%)	40	(40%)
		Trace	30	(30%)	30	(30%)
		1+	5	(5%)	5	(5%)
		2+	2	(2%)	4	(4%)
		3+	0		0	

USER ID: directory/program.sas DDMMYYYY hh:mm

CONFIDENTIAL

206817

Example: EG1

Protocol: GSK123456

Population: xxxxx

Page 1 of n

Table x.x

xxxxxxxxxxxxxxxxxxxxxxxxxxxxxx

	Treatment A (N=157)	Treatment B (N=160)
Time Period 1		
n	156	160
Normal	81 (52%)	90 (56%)
Abnormal, not clinically significant	75 (48%)	69 (43%)
Abnormal, clinically significant	0	1 (<1%)
Time Period 2		
n	117	123
Normal	50 (43%)	67 (54%)
Abnormal, not clinically significant	64 (55%)	55 (45%)
Abnormal, clinically significant	2 (2%)	1 (<1%)
n	117	122
Clinically significant change from baseline	2 (2%)	1 (<1%)
Not a clinically significant change	115 (98%)	121 (>99%)
Not applicable	0	0

USER ID: directory/program.sas DDMMYY YYYY hh:mm

CONFIDENTIAL

206817

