Example: EG1 (continued)

Protocol: GSK123456

Population: xxxxx

Page 1 of n

Table x.x

xxxxxxxxxxxxxxxxxxxxxxxxxxxxxx

	Treatment A (N=157)	Treatment B (N=160)
Any time post-baseline		
n	117	123
Normal	50 (43%)	67 (54%)
Abnormal, not clinically significant	65 (56%)	55 (45%)
Abnormal, clinically significant	2 (2%)	1 (<1%)
No result (not available)	0	0
n	117	122
Clinically significant change from baseline	2 (2%)	1 (<1%)
Not a clinically significant change	115 (98%)	121 (>99%)
Not applicable	0	0

USER ID: directory/program.sas DDMMYY YYYY hh:mm

CONFIDENTIAL

206817

Example: EG2

Protocol: GSK123456

Population: xxxxx

Page 1 of n

Table x.x
xxxxxxxxxxxxxxxxxxxxxxxxxxxxxx

		Planned Relative Time		n	Mean	SD	Median	Min.	Max.
Heart Rate (bpm)	Trt A	200	Time 1	200	91.6	11.32	90.0	68	140
			Time 2	190	92.4	9.83	90.0	70	122
			Time 3	186	92.6	10.87	89.0	72	125
	Trt B	200	Time 1	200	91.6	11.32	90.0	68	140
			Time 2	190	92.4	9.83	90.0	70	122
			Time 3	186	92.6	10.87	89.0	72	125
PR Interval (msec)	Trt A	200	Time 1	200	91.6	11.32	90.0	68	140
			Time 2	190	92.4	9.83	90.0	70	122
			Time 3	186	92.6	10.87	89.0	72	125
	Trt B	200	Time 1	200	91.6	11.32	90.0	68	140
			Time 2	190	92.4	9.83	90.0	70	122
			Time 3	186	92.6	10.87	89.0	72	125

USER ID: directory/program.sas DDMMYYYY hh:mm

CONFIDENTIAL

206817

Example: VS1

Protocol: GSK123456

Population: xxxxx

Page 1 of n

Table x.x
xxxxxxxxxxxxxxxxxxxxxxxxxxxxxx

	Treatment	N	Planned	n	Mean	SD	Median	Min.	Max.
			Relative Time						
Systolic BP (mmHg)	Trt A	200	Time 1	200	91.6	11.32	90.0	68	140
			Time 2	190	92.4	9.83	90.0	70	122
			Time 3	186	92.6	10.87	89.0	72	125
	Trt B	200	Time 1	200	91.6	11.32	90.0	68	140
			Time 2	190	92.4	9.83	90.0	70	122
			Time 3	186	92.6	10.87	89.0	72	125
Diastolic BP (mmHg)	Trt A	200	Time 1	200	91.6	11.32	90.0	68	140
			Time 2	190	92.4	9.83	90.0	70	122
			Time 3	186	92.6	10.87	89.0	72	125
	Trt B	200	Time 1	200	91.6	11.32	90.0	68	140
			Time 2	190	92.4	9.83	90.0	70	122
			Time 3	186	92.6	10.87	89.0	72	125

USER ID: directory/program.sas DDMMYYYY hh:mm

CONFIDENTIAL

206817

Example: AE7
Protocol: GSK123456
Population: xxxxx

Page 1 of n

Listing x.x
xxxxxxxxxxxxxxxxxxxxxxxxxxxxxx

System Organ Class Preferred Term	Treatment	No. with Event	Unique Subject Id.
Gastrointestinal disorders Dyspepsia	Placebo	9	PPD
	Treatment A	11	
	Treatment B	4	
Nausea	Placebo	6	
	Treatment A	8	
	Treatment B	4	

USER ID: directory/program.sas DDMMYY YYYY hh:mm

CONFIDENTIAL

206817

Example: AE9CP
 Protocol: GSK123456

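### SAP 10.4.4 bars unscheduled and out-of-window results from summaries with no exception for the worst-case laboratory and any-time ECG rows, so these rows omit a subject whose abnormality in a period is seen only at such a visit

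*SAP*

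**What the plan says.** SAP 10.4.4 sets two general exclusions. On unscheduled visits: "Unscheduled visits will not be included in summary tables". On late or early visits: "Visits outside the protocol defined time-windows (i.e. recorded as protocol deviations) will be included in listings but omitted from figures, summaries and statistical analyses". Both kinds of result are kept in listings.

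SAP 10.9.5 assigns shell LB4 to the chemistry and haematology shift tables (2.11, 2.14, 2.17, 2.20) and shell EG1 to the ECG findings tables (2.25, 2.28). The programming notes for all six are blank. In SAP 10.10.2, LB4 has a row labelled "Worst Case Post-Baseline" and is laid out by analyte and treatment ("Test= Alanine Aminotransferase (IU/L), Treatment=Treatment A"). EG1 has a block labelled "Any time post-baseline".

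The nearest thing to an exception is in SAP 10.5.1, which says that subjects with both high and low values "at any post-baseline visits for safety parameters will be counted in both the High and Low categories of" an any-visit row. It settles double counting and does not mention unscheduled or out-of-window results. SAP 10.6.1 says that available planned data from withdrawn subjects go into tables unless otherwise specified.

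**The concern.** A row labelled worst case or any time will be read as a complete count, by treatment, of subjects with an abnormal result after dosing. Under the general exclusions it covers scheduled, in-window results only.

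The protocol expects other results to exist. Section 9 allows unscheduled samples for safety reasons, Appendix 2 allows additional tests at any time, and Appendix 4 provides for further tests to clarify an adverse event. Such a sample need not repeat an analyte already known to be abnormal. LB4 is built analyte by analyte, so the only out-of-range value of a different analyte can fall on it.

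At stake is the completeness of six safety tables in a study whose objectives include safety and tolerability and whose columns hold 12 to 18 subjects.

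**Working it through.** There is no stated figure to reproduce. The check traces the rule to the rows and counts the scheduled results that feed them.

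**What the rule does to one subject, one analyte, one period**

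- Scheduled values in range, one unscheduled value out of range: omitted from the worst-case row.
- Unscheduled value out of range, later scheduled value in the same period out of range in the same direction: counted.
- Scheduled value out of range, then unscheduled repeats: counted already.
- Abnormality arising after Day 3 and persisting to the next Day -1: measured there, but that day belongs to the next period (SAP 10.3.1) and is its baseline (SAP 10.4.3.1). It is not counted under the treatment after which it arose.

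The same logic applies to abnormal ECGs. The only post-dose visit window found in the documents is the follow-up visit, 7 days ± 1 day, so the out-of-window route mainly concerns that visit.

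**Scheduled post-dose laboratory samples, continuing subjects (SAP 10.2)**

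Part 1: Periods 1 and 2 have one each (Day 3); Period 3 has two (Day 4, follow-up). Part 2: Period 1 has one (Day 3); Period 2 has two (Day 3, follow-up).

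| Column | Subjects | Samples | Subject-periods with one sample |
|---|---|---|---|
| 10 mg | 12 | 12×1 = 12 | 12 of 12 |
| 50 mg | 12 | 12×1 = 12 | 12 of 12 |
| 100 mg | 12 | 12×2 = 24 | 0 of 12 |
| Placebo | 18 | 6×1 + 6×1 + 6×2 = 24 | 12 of 18 |
| Part 2 fed | 16 | 8×1 + 8×2 = 24 | 8 of 16 |
| Part 2 fasted | 16 | 8×1 + 8×2 = 24 | 8 of 16 |

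Part 1 gives 36 of 54 and Part 2 gives 16 of 32. Together that is 52 of 86, or 60%. In those subject-periods the worst-case row can only repeat Day 3.

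**The gap.** With at least 7 days between doses, the next dose falls on Day 8 at the earliest and the next Day -1 on Day 7. In Part 1 Periods 1–2 and Part 2 Period 1, a sample on Days 4 to 6 belongs to the treatment just given but can only be unscheduled.

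**ECGs are less exposed.** Part 1 has three scheduled post-dose ECGs in Periods 1 and 2 and five in Period 3. That gives 12×3 = 36 (10 mg), 12×3 = 36 (50 mg), 12×5 = 60 (100 mg) and 6×3 + 6×3 + 6×5 = 66 (placebo). Part 2 has three in Period 1 and four in Period 2, or 8×3 + 8×4 = 56 per condition.

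**Scale of one omitted subject.** 1/12 = 8.3 points in a Part 1 dose column, 1/18 = 5.6 in placebo, and 1/16 = 6.3 in a Part 2 column. At n = 12 a row would show 0/12 (exact 95% limits 0 to 26.5%) where the full data give 1/12 (0.2 to 38.5%).

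**The case against.** The strongest reply is that little is lost. Every value stays in a listing, and subjects with a value of potential clinical importance have dedicated listings. Protocol 9.3.5 and Appendix 4 have clinically significant results recorded as adverse events, and SAP Section 7 counts those arising in washout under the preceding period. Subjects who discontinue have the follow-up assessments. All this stands and limits the point to results not judged clinically significant. It does not remove it, because a shift table counts values against the normal range whatever the clinical judgement.

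Second, LB4 and EG1 are generic examples, with time points such as Week 4 that this study lacks, and the any-visit label in SAP 10.5.1 matches no shell. That is fair: the rows might not be produced in this form. But the SAP names these shells as the layouts for the six tables, and nothing in it drops the rows.

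Third, company reporting standards might govern how such rows are derived. They are not in the documents and cannot be checked. SAP 10.4.4 applies them unless otherwise stated, and it states the exclusions itself.

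Fourth, 10.4.4 speaks of unscheduled visits, and an extra sample taken while a subject is resident is not plainly a visit. Several readings at one time point also have their own rule in 10.5.1. This ambiguity is real for the in-house days, but does not help between discharge and the next admission.

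Finally, the rule is prespecified and identical for active and placebo columns, and admitting extra samples gives more chances of being counted to those sampled more often. That is a genuine cost of the fix.

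**Conclusion.** The point holds as a minor incompleteness of six safety tables. A subject is omitted when the abnormality, in a given direction for a given analyte, or the abnormal ECG, is seen at no scheduled, in-window time in that period. In Part 1 Periods 1–2 and Part 2 Period 1, the single Day 3 laboratory sample leaves a continuing subject no later scheduled value in the period to recover it.

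Four stronger readings may tempt a reader, and the documents do not support them:

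- That a subject is missed whenever the first abnormal result is unscheduled. The rows count a category over the period, so a later scheduled abnormality in the same direction brings the subject in.
- That 60%, or the 5.6 to 8.3 points, measure loss. The first describes the sampling schedule and the second is one subject over the column size. No frequency is given and none is assumed.
- That the tables are tilted towards the drug. An omission can only lower the count in its own column, but the rule applies to every column alike and nothing indicates a direction between treatments.
- That SAP 10.6.1 forbids unplanned data from withdrawn subjects. It says planned data are included; it does not say that only planned data are.

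The conclusion assumes that the six tables are produced with the rows shown in their shells and that 10.4.4 is applied as written.

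**What to change.** Keep the by-visit rows as planned. Add one sentence to SAP 10.4.4: any worst-case or any-time post-baseline row in Tables 2.11, 2.14, 2.17, 2.20, 2.25 and 2.28, including the any-visit row named in 10.5.1 if it is produced, uses all post-baseline values in the period as assigned by 10.3.1. Say that this covers unscheduled and out-of-window values and applies to withdrawn subjects too. Footnote the six tables accordingly.

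The cost is the sentence, the footnotes and minor programming. The downside is that the rows may look slightly less favourable and that subjects sampled more often have more chances to be counted; the footnote should make that visible.

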10.5. Appendix 5: Derived and Transformed Data
10.5.1. General

Multiple Measurements at One Time Point
 
 Mean of the measurements will be calculated and used in any derivation of summary statistics but if listed, all data will be presented. If there are two values within a time window the value closest to the target day for that window will be used. If values are the same distance from the target, then the mean will be taken. Subjects having both High and Low values for Normal Ranges at any post-baseline visits for safety parameters will be counted in both the High and Low categories of “Any visit post-baseline” row of related summary tables. This will also be applicable to relevant Potential Clinical Importance summary tables.
Study Day

 Calculated as the number of days from start of dosing date: 
 Ref Date = Missing → Study Day = Missing Ref Date < of start of dosing Date → Study Day = Ref Date – of start of dosing Date Ref Date ≥ of start of dosing Date → Study Day = Ref Date – (of start of dosing Date) + 1
10.5.2. Study Population
Demographics
Age

 GSK standard IDSL algorithms will be used for calculating age where birth date will be imputed as: 
 Any subject with a missing day will have this imputed as day ‘15’. Any subject with a missing date and month will have this imputed as ‘30th June’. Birth date will be presented in listings as ‘YYYY’. Reference will be Randomization date for Part 1 and Part 2 Reference date for calculation of age at screening will be from visit 1 (Screening visit) date, however this will be from screen failure date for a screen failure subject. Analysis age group will be categorized (Years): <=18, 19-64, 65-74, >=75 Age will be categorized for EudraCT: <=17 years, 18-64 years, 65-84 years, >=85 years
Body Mass Index (BMI)

 Calculated as Weight (kg) / [Height (m)²]

10.5.3. Safety

Laboratory Parameters	

 If a laboratory value which is expected to have a numeric value for summary purposes, has a non-detectable level reported in the database, where the numeric value is missing, but typically a character value starting with '<x' or '>x' (or indicated as less than x or greater than x in the comment field) is present, the number of significant digits in the observed values will be used to determine how much to add or subtract in order to impute the corresponding numeric value. 
 Example 1: 2 Significant Digits = '< x ' becomes x – 0.01 Example 2: 1 Significant Digit = '> x' becomes x + 0.1 Example 3: 0 Significant Digits = '< x' becomes x – 1 	

Laboratory Assessments	
Haematology	Platelet Count, RBC Count, Haemoglobin, Hematocrit, RBC Indices (MCV, MCH, %Reticulocytes), WBC count with Differential (Neutrophils, Lymphocytes, Monocytes, Eosinophils, Basophils)
Clinical Chemistry	BUN, Creatinine, Glucose (fasting), Uric acid, HDL-cholesterol, Amylase, Potassium, Sodium, Calcium, TG, LDH, Chloride, Aspartate Aminotransferase (AST), Alanine Aminotransferase (ALT), Alkaline phosphatase, Total Cholesterol, GGT, Phosphorus, Total and direct bilirubin, Total Protein, Albumin, LDL-cholesterol, CK (CPK)
Routine Urinalysis	
 Specific gravity, pH (assessed by dipstick) glucose, protein, blood, ketones, bilirubin, urobilinogen by dipstick Microscopic examination (if blood or protein is abnormal)

ECG (12-lead ECG)
ECG findings, ECG values (Heart rate, PR interval, QRS duration, QT interval and QTcF intervals)

Vital Signs
Pulse rate, Blood pressure (Systolic, Diastolic), Temperature

Ophthalmic examinations
Ophthalmic examinations

